12.4 Procedures for verification, validation and securing of electronic data systems

The Clinical Data Management System (CDMS) is hosted on a dedicated database server at the vendor MedNet Solutions, Inc. Only authorized users with fixed roles have access to the Clinical Data Management System (CDMS). The access is controlled and maintained by the Clinical Data Management. Every access is automatically logged and changes of the clinical data are stored in independent audit trails. The CDMS is verified and validated accordingly. The user interface and the internal business logic is validated accordingly and verified during the study related development and before release for data entry.

An authenticated user account is created and maintained by BIOTRONIK for each authorized user once the user has completed appropriate training. Users are obligated to keep their password confidential.

Depending on their role within the investigational study, users are limited to 'read only' or may be given permits to enter or update data, provide resolutions to queries and apply electronic signatures. Only investigators are allowed to sign the entries.

12.5 Data retention and archiving

All study related electronic documents are stored in the archive of BIOTRONIK which provides storage conditions free from risk of fire, flood, theft and vermin. The access to the files is controlled.

After CDMS closure, all eCRF data and the audit trail and other relevant CDMS contents are exported and stored electronically for at least 15 years on the archive server.

At the end of this period, requirements from laws and other regulations will be reconsidered in order to decide whether the retention period must be extended or data must be deleted.

All relevant study related documents have to be stored in the Investigator Site File. Documents containing patient's data, raw data and other study related documents have to be archived in the investigational site. In case of electronic source data (e.g. electronic patient files) adequate actions have to be taken to ensure data availability during the whole archiving period.

13 AMENDMENT PROCEDURES

If throughout the course of the study changes to the Clinical Investigation Plan (CIP) are deemed to be necessary, a change justification has to be prepared which includes the rationale and content of the adjustment. The modification of the CIP can either be summarized in a separate document as an attachment to the current applicable version of the CIP **or** result in a new version of the CIP.

If the changes have impact on study related procedures or data analysis they are substantial by definition.

New versions of the CIP or substantial amendments have to be reviewed and confirmed by the Coordinating Investigator. All principle investigators have to acknowledge the receipt of an amendment by either signing the CIP acknowledgement page which is part of the CIP, or by signing the amendment agreement form if no new version was created.

Before implementation of any changes, substantial amendments have to be approved by the Ethics Committee (EC) and – if applicable – by the Competent Authority (CA). Non substantial amendments are submitted for notification only.

The investigator should not implement any deviation from or changes to the CIP without agreement of the sponsor and prior review and documented approval from the EC (and CA if required). The only exception is the necessity to eliminate an immediate hazard to the subjects, or when the change involves only logistical or administrative aspects of the study.

14 DEVIATIONS FROM CLINICAL INVESTIGATION PLAN

14.1 CIP compliance and exceptions

All sponsor personnel, all investigational site personnel as well as other third parties, who are involved in tasks covered by this CIP, are generally obliged to comply with this CIP.

A **deviation** is any failure to follow, intentionally or unintentionally, the requirements of the CIP, including laws, guidelines and other regulation as far as required by the CIP and applicable laws, as well as applicable amendments. Deviations that are likely to seriously affect or that actually have seriously affected the rights or safety or wellbeing of subjects or the scientific integrity of the clinical investigation are **major** deviations. Otherwise they are **minor** deviations.

Erroneous, spurious or missing data in a CRF is not a deviation in itself and is handled according to the query processes described in the data management section of this CIP. However, the underlying reason might be a deviation.

Under **emergency** circumstances, deviations from the CIP to protect the rights, safety and well-being of human subjects may proceed without prior approval of the sponsor and the ethics committee.

No waivers from the CIP are allowed.

14.2 Recording, reporting and analyzing deviations

All deviations are recorded and reported electronically in the CDMS system iMedNet. If the eCRF logic has detected a CIP deviation based on the data entry, deviation forms are triggered automatically by iMedNet. Additionally, deviation forms can be created manually via iMedNet by the site or by the sponsor personnel.

14.2.1 Site specific deviations

Investigational sites are obliged to record any deviation immediately as they become aware of it. In addition, compliance to the CIP is verified by the sponsor through monitoring visits. Each site specific deviation is assessed for the need of corrective or preventive actions.

14.2.2 Other deviations

Deviations by sponsor personnel or third parties shall be reported immediately to the sponsor by anyone who becomes aware of it. They are recorded in the CDMS system iMedNet, and assessed for the need of corrective or preventive actions.

14.2.3 Reporting

Deviations are reported in the interim and final clinical investigation reports.

14.3 Notification requirements and timelines

The sponsor records specific notification requirements of the involved ethics committees and competent authorities and assures that the required timelines are respected.

14.4 Actions

Actions are taken in order to repair or to avoid any negative consequences caused by a deviation. Furthermore, actions are taken to avoid that the same sort of deviation reappears.

Every individual deviation is assessed by the sponsor for the need of appropriate action. In addition, the sponsor regularly evaluates the overall study deviation report to identify the need of general preventive actions.

All persons involved in a deviation have to co-operate with the sponsor in identifying and implementing the appropriate actions. Performance and implementation of these actions are

documented in iMedNet and later filed in the **central file** and, in the case of site specific deviations, in the respective **investigator site file**.

Disqualification of study personnel or investigational sites is the ultimate escalation step of preventive actions. This means that in case of major deviations that seriously affect the safety and well-being of subjects or that bear a high risk of refusal of the clinical data and mistrust to the results of the study and that are likely to reappear despite other actions, the responsible person or investigational site is excluded from further conduct of the study, unless this action would jeopardize the rights, safety or welfare of the patients.

15 DEVICE ACCOUNTABILITY

All devices used in this clinical study carry a CE mark and will be used within their intended use. Therefore special device accountability procedures are not applicable for countries located in the EU. However, the inserted BIOMONITOR III are identifiable by an unique serial number. This number will be recorded on the insertion eCRF form. By need or at least at the end of the study, a list with all used devices will be created.

Participating sites outside of the CE area will only use the devices after market approval or approval for the Master Study by the respective regulatory institution according to national regulations.

Note: The BIOMONITOR III as well as Remote Assistant III are not yet listed on the Australian Register of Therapeutic Goods. The study will be conducted under the CTN scheme in Australia. The devices provided to the investigators at Australian sites will be labelled as investigational devices and must not be used in routine care until TGA approval.

BIOMONITOR III which are not approved for an overall market release in non-EU countries and are labeled 'exclusively for clinical investigation' have to be stored under special conditions.

The sponsor keeps records to document the physical location of all investigational devices including the shipment of investigational devices to the investigational sites or to the local units, usage, storage and return. An electronic device accountability log is used for the documentation of the whole process.

Access to investigational devices is controlled and the devices are used in the clinical investigation only and according to the CIP.

The principal investigator or an authorized designee shall keep records documenting the receipt, storage, usage and return of the investigational devices. The electronic device accountability log is used for this site specific documentation.

The responsible field CRA checks the storage, usage and documentation and verifies the completeness of the device accountability log in the CDMS regularly during his/her visits.

After the closure of the study, the summary of this log will be used for the final report.

16 STATEMENT OF COMPLIANCE

16.1 Applicable ethical standards

The study will be conducted in compliance with the principles that have their origin in the Declaration of Helsinki (current version). Each step in the clinical investigation, from the initial consideration of the need and justification for the study to the publication of the results, if any, will be carried out in accordance with recognized ethical principles.

The study will be registered at the publicly accessible database ClinicalTrials.gov.

16.2 Applicable international and national standards

The study will be conducted in compliance with the international standard ISO 14155:2011 "Clinical investigation of devices for human subjects – Good clinical practice".

In deviation to ISO 14155:2011, no dedicated Investigator's Brochure is provided to sites that accept CE mark, because the investigational device will only be made available after CE approval, and therefore the Instructions for Use (IFU) are considered as sufficient.

The study will also be conducted according to the applicable national legal requirements of the participating investigational sites.

16.3 Ethics committee and competent authority

The study will not begin at an investigational site until favorable opinion of the responsible ethics committee has been obtained for that site and approval of the competent authority (if applicable) has been granted for the conduct of the study in the respective country.

16.4 Statement of adherence to additional requirements

If any additional requirements will be imposed by an ethics committee or a competent authority, these requirements will be followed, if appropriate.

16.5 Statement on subject insurance

All participants of this clinical study are insured against study related injury according to applicable provisions of law.

The insurance of the sponsor does not relieve the investigator and the collaborators of any obligation to maintain their own liability policy.

17 INFORMED CONSENT PROCESS

A patient information form including the informed consent form has been prepared by the Project Manager. The content of this document needs to be reviewed and approved by the ethics committee, and suggested changes need to be implemented.

17.1 General considerations

The informed consent procedure is performed by the Principal Investigator or any investigator designated for this task as recorded in the delegation of duties log. The investigator has to fully inform the patient of all pertinent aspects of the clinical investigation in language and terms she/he is able to understand. Special attention has to be paid to the individual information needs of the patient, and the appropriate methods used for the interview. The investigator has to verify that the patient has understood all information. The patient is given adequate time to consider his or her decision to participate in the clinical investigation.

When the patient agrees in the study participation, the patient personally writes the date and signs on the informed consent form. Afterwards, the investigator who performed the informed consent discussion writes the date and signs on the informed consent form. Both parties should sign on the same day. By signing the informed consent form, the patient is included in the study. Pre-screening of the patient chart in respect to the inclusion and exclusion criteria is not a study specific procedure.

Date and time of the informed consent discussion as well as date and time of patient's signature of the informed consent form should be documented in patient's medical record. A copy of the signed and dated written informed consent form is provided to the patient. Both signatures need to be obtained before any study related procedure. The investigator ensures that no subjects are included in this clinical study who are unable to give informed consent by selecting patients with age ≥ 18 years, who understand the nature of the procedure.

If during the course of the clinical investigation new information emerges, the investigator informs the patient accordingly. If this information concerns safety aspects or other aspects that could influence the decision of the patient to continue participating in the study, the patient shall be informed immediately.

Each informed consent form contains the emergency contact details for the respective principal investigator.

17.2 Special circumstances for informed consent

Not applicable.

18 ADVERSE EVENTS AND DEVICE DEFICIENCIES

In the course of the clinical investigation, undesired medical events can occur in participating patients, which are called adverse events (AEs) in the following. Furthermore, device deficiencies (DD) may also be observed. All AEs and DDs of the investigational device shall be assessed by the investigator and shall be documented and reported throughout the clinical investigation within the timelines defined below.

The investigator shall document all events on the respective eCRF pages provided within the clinical data management system (CDMS). The indicated timelines for reporting of initial cases and possible update reports shall be strictly followed.

According to ISO 14155:2011 events will be classified on the basis of the definitions below.

18.1 Definition of adverse events

An AE is defined* as any untoward medical occurrence, unintended disease or injury, or untoward clinical signs (including abnormal laboratory findings) in subjects, users or other persons whether or not related to the investigational device. This includes:

- Events related to the investigational device or the comparator
- Events related to the procedures involved
- For users or other persons, this definition is restricted to events related to the investigational devices.

Symptoms of the **known diseases** of the subject, like syncope with uncertain origin or atrial fibrillation, which were present already before participation in the study and do not change in frequency or severity during the course of the study are **no AE**. Also **planned** subsequent processing, like BIOMONITOR III explantation, implantation of a pacemaker, ICD or CRT device, or ablation, are **no AE**.

*see ISO 14155 3.2

18.2 Definition of adverse device effects

An adverse device effect (ADE)* is an AE that is related to the use of an investigational device. This includes any AE resulting from insufficient or inadequate instructions for use or the deployment, insertion, installation, or operation, or any malfunctioning of the investigational device and any event resulting from use error or from unintentional misuse of the investigational device.

*see ISO 14155 3.1

18.2.1 Causality Assessment

The relationship between the use of the investigational device (including the medical-surgical procedure) and the occurrence of each adverse event shall be assessed and categorized, considering the presence of confounding factors, such as concomitant medication and treatment, the natural history of the underlying disease, other concurrent illness or risk factors.

Each AE will be classified according to five different levels of causality. As defined in the Meddev 2.7/3 rev 3, the investigator will use the following definitions to assess the relationship of the serious adverse event to the investigational device or procedures and the sponsor will review the investigator's categorization:

Not related: the relationship to the device or procedures can be excluded.

Unlikely: the relationship with the use of the device seems not relevant and/or the event can be reasonably explained by another cause, but additional information may be obtained.

Possible: the relationship with the use of the investigational device is weak but cannot be ruled out completely. Alternative causes are also possible (e.g. an underlying or concurrent

illness/clinical condition or/and an effect of another device, drug or treatment). Cases were relatedness cannot be assessed or no information has been obtained should also be classified as possible.

Probable: the relationship with the use of the investigational device seems relevant and/or the event cannot be reasonably explained by another cause, but additional information may be obtained.

Causal relationship: the serious event is associated with the investigational device or with device procedures without reasonable doubt.

The investigators will distinguish between adverse events related to the investigational device and those related to the device procedures (any procedure specific to the investigational device). Procedure related events refer to the procedure related to the application of the investigational device only and therefore not to any other procedure for other devices and not to any other procedures or treatments applied later throughout the clinical investigation, for instance to treat (serious) adverse events. In case of a replacement of the investigational device in response to an adverse event (e.g. lead replacement after dislocation), the replacement will be considered like an initial application of a new investigational device and shall be assessed accordingly.

An adverse event can be related both to the procedure and the investigational device. Complications of procedures are considered not related if the said procedures would have been applied to the patient also in the absence of investigational device use or its application.

18.3 Definition of device deficiency

Device deficiency (DD)* is defined as inadequacy of a device with respect to its identity, quality, durability, reliability, safety, or performance, including malfunctions, use errors and inadequate labeling.

*see ISO 14155 3.15

DDs of the investigational device shall be documented throughout the study. DDs which caused an adverse event are reported on the respective adverse event form. In case the DD did not cause an adverse event the provided DD form shall be used to document this "non-medical" event.

If a DD could have led to an SADE

- if either suitable action had not been taken,
- if intervention had not been made, or
- if circumstances had been less fortunate,
- the DD is classified as DD with SADE potential.

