18.7 Anticipated adverse events

The following peri- or post-operative risks are anticipated with the insertion and also during the post-insertion phase including explantation of the BIOMONITOR III and are therefore assessed as adverse device effects. They are listed in Table 4 as sorted by their incidence rates. For all references used for this chapter, refer to the list at the end of this section. In addition to the planned ICM insertion patients will undergo a non-invasive 48-hours Holter-Monitoring. Risks of Holter-Monitoring are rare but may include skin irritation at the application site of the adhesive electrode patches.

Table 4: Anticipated AEs based on literature research sorted by incidence rate.

Frequency	Event Type	Reference ID
Frequent 1 to 10 patients out of 100	Insertion site irritation/soreness	4, 9
	Insertion site erosion	3, 9
	Insertion site pain	1, 2, 3, 5, 8, 11
	Insertion site dehiscence/device protrusion/extrusion	2, 7, 13, 15
	Insertion site infection	1, 2, 3, 5, 6, 7, 8, 9, 10, 11, 12, 15
	Insertion site hematoma	3, 7, 14
Occasionally 1 to 10 patients out of 1.000	Insertion site hemorrhage	1, 8, 13
	Insertion site discomfort	5, 12
	Insertion site bruising	2, 13
	Incision site complication	8, 13
	Device dislodgement/migration	3, 5, 13, 14
Not known Frequency not assessable on the basis of the available data	Oversensing, Undersensing, Premature battery depletion, Electromagnetic interference (EMI), Impaired healing, Insertion site rash, Non-insertion site rash, Non-insertion site pain, Numbness of upper arm, Procedural dizziness, Post procedural dizziness, Post procedural nausea, post procedural headache, Dyspnea, Vagal reaction, Presyncope, Supraventricular tachycardia, Shock/dyspnea (reaction to antibiotic administration prior to device insertion), Device interrogation issue, Home Monitoring transmission incomplete/missing, Housing surface conspicuous before implantation/insertion, Varying P/R values, Device in safety back-up mode, Silicone coating damaged, Foreign body rejection phenomena, Accumulation of fluid in the device pocket	1, 2, 3, 5, 6, 13, 16, 17

1. BIOTRONIK. CIR Master Study of the Implantable Cardiac Monitor BioMonitor 2015.
2. BIOTRONIK. CIR BioMonitor 2 Pilot Study 2016.
3. BIOTRONIK. CIR BIO|MASTER.BioMonitor 2 2017.

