18.8 Reporting responsibilities

18.8.1 Reporting responsibilities of the investigator to sponsor

The investigator shall document all events on the respective eCRF pages provided within the CDMS. The indicated timelines for reporting of initial cases and possible update reports shall be strictly followed (see section 18.9).

All AEs and ADEs) shall be reported together with an assessment by completing the AE-CRF in accordance with ISO 14155:2011.

For device deficiencies of the investigational device, a DD-CRF shall be completed.

The reports shall be done with all information available, even if this results in an incomplete report. The investigator has to follow-up ongoing Events either as long as the patient participates in the study, the clinical investigation is terminated prematurely or until the event has been resolved, whatever comes first. Ongoing SADEs related to the investigational device will be followed for a maximum time period of either 4 weeks after pre-mature or regular study termination of the individual patient. This also applies to Adverse Events involving the explantation or replacement of an investigational device, heart transplantation or implantation of a ventricular assist device. This follow-up period is reduced if 'Last Patient Out' is announced in the study. All follow-ups on open adverse events will stop at this point in time at the latest.

Multiple events may occur simultaneously in one subject. For each medically independent event an individual report must be provided.

In addition, the action taken/treatment should also be provided with any supportive documentation available.

The investigator has to ensure that all relevant information is available. This also includes information from other parties (family, other hospitals etc.).

If a patient dies during the study this might be subject to special reporting requirements in some countries. Therefore as much information as possible should be provided to enable BIOTRONIK to explain the circumstances leading to death. At least a pseudomized copy of the death records and an autopsy report (if performed) should be sent to BIOTRONIK promptly. All actions taken, which were initiated to gain further information must be documented in writing and provided to BIOTRONIK.

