18.9 Reporting timelines

The reporting timelines for the investigator are displayed in Table 5.

Table 5: Reporting timelines.

Event	Report to	Timeline
Adverse Event (AE) / Adverse Device Effect (ADE)	CCR BIOTRONIK SE & Co. KG: Documentation in the AE CRF	Preferably within 2 weeks
Serious Adverse Event (SAE) / Serious Adverse Device Effect (SADE)	CCR BIOTRONIK SE & Co. KG: Documentation in AE-CRF	Immediately, latest 24h after detection
Unanticipated Serious Adverse Device Effect (USADE)	CCR BIOTRONIK SE & Co. KG: Documentation in AE-CRF	Immediately, latest 24h after detection
Device Deficiencies	CCR BIOTRONIK SE & Co. KG: Documentation in the DD-CRF	Preferably within 14 days
Device Deficiency with SADE potential	CCR BIOTRONIK SE & Co. KG: Documentation in DD-CRF	Within 24 hours

The obligation to assess and report SA(D)Es and Serious Device Deficiencies to the sponsor without unjustified delay is an important part of the Principal Investigator's responsibilities as defined by ISO 14155:2011. This obligation is not restricted to scheduled patient follow ups according to the CIP, but it is a continuous responsibility for the duration of the study, making sure that any unexpected risks originating from the study procedures or the investigational product are identified as soon as possible and patients are adequately protected. The Principal Investigator is responsible to set up appropriate workflows at his/her site, making sure that:

- the site study team is continuously informed on any relevant interactions or interventions concerning study patients at the site, regardless if members of the study team are directly involved or not;
- if the site is part of a larger organizational structure - e.g. a multi-faculty-hospital - a notification system is in place, making sure that other departments/clinics are aware of the patient's study participation and that relevant events, such as hospitalizations, are notified to the site study team without delay;
- if information on relevant events from external sources reaches the site (e.g. medical reports from other facilities), these are made available to the study team without delay.

Note: in this context the site is defined as the organizational unit (e.g. a hospital or a department/clinic within a multi-faculty-hospital), which serves as BIOTRONIK's contract partner for the study. Information that is part of the medical records hosted by the site is considered as known to the study team and subject to reporting.

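### CIP sections 9.8, 18.3, 18.7, 18.8.1 and Table 5 give conflicting instructions for recording a device fault, so deficiency counts may differ by site and the deadline for some faults with SADE potential is ambiguous

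*Protocol*

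**What the plan says.** Five places in the CIP bear on how a device fault is recorded.

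- **Section 18.3** divides deficiencies by consequence: "DDs which caused an adverse event are reported on the respective adverse event form". For the rest, "In case the DD did not cause an adverse event the provided DD form shall be used to document this" kind of event, which the section describes as non-medical. It then defines SADE potential with the words "If a DD could have led to an SADE" and does not limit this class to deficiencies without an AE.
- **Section 18.8.1** sends AEs and adverse device effects (ADEs) to the AE form. It then adds, without exception: "For device deficiencies of the investigational device, a DD-CRF shall be completed".
- **Table 5 (section 18.9)** places ordinary deficiencies on the DD form, preferably within 14 days. The row "Device Deficiency with SADE potential" is also on the DD form, within 24 hours. AEs and ADEs go on the AE form, preferably within two weeks; serious ones go on the AE form within 24 hours of detection.
- **Section 18.7** introduces the risks in Table 4 as anticipated "and are therefore assessed as adverse device effects". The table includes premature battery depletion and also "Device interrogation issue, Home Monitoring transmission incomplete/missing, Housing surface conspicuous before implantation/insertion, Varying P/R values, Device in safety back-up mode, Silicone coating damaged".
- **Section 9.8** requires a deficiency that occurs at an interim follow-up to be documented on the AE form.

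Section 18.1 defines an AE as a medical occurrence, disease, injury or clinical sign, and section 18.2 makes an ADE a subset of AEs. SAP section 15 has no counting rule for deficiencies; it takes AEs and deficiencies as they come from the vigilance department's safety report.

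**The concern.** These are working instructions to sites, and they do not agree. One site may put a deficiency that caused an AE on the AE form only, following 18.3. Another may complete a DD form as well, following 18.8.1. A missed transmission with no effect on the patient may be a deficiency at one site and an ADE at another.

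The study is a post-market follow-up meant to identify residual device risk (CIP 7.1), and AEs and deficiencies are listed data of interest (CIP 7.5, SAP 15). If filing depends on which section a site reads, the DD and ADE counts partly reflect filing habits rather than device behaviour. The form and the classification also decide which row of Table 5 a site looks up. That matters for faults with SADE potential, because the sponsor has to report them to authorities where local rules require it (CIP 18.8.3) and depends on sites to identify them.

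**Working it through.** No sample size, power or error rate enters this point, and the plan states no figure to reproduce. The check takes each kind of fault through the sections and reads off its form and deadline.

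| Case | 18.3 | 18.8.1 and Table 5 | Deadline in Table 5 |
|---|---|---|---|
| 1. No AE, not in Table 4 | DD form | DD form | No conflict |
| 2. No AE, listed in Table 4 | DD form | DD form, but AE form if treated as an ADE under 18.7 | With SADE potential: 24 hours (DD row) or preferably two weeks (ADE row). Otherwise 14 days or two weeks, which is the same |
| 3. Non-serious AE, no SADE potential | AE form | DD form as well as AE form | 14 days or two weeks, the same |
| 4. Non-serious AE, SADE potential | AE form | DD form as well as AE form | 24 hours (DD row) or preferably two weeks (AE/ADE row) |
| 5. Serious AE | AE form | DD form as well as AE form | 24 hours on either route |

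Section 9.8 cuts across the table. At an interim visit even cases 1 and 2 go on the AE form. It changes the form only; it does not reclassify the fault, so it does not by itself alter the deadline.

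**Table 4 against the AE definition.** At least six of the listed items involve no medical occurrence of their own: premature battery depletion, interrogation issue, incomplete or missing transmission, conspicuous housing before implantation, safety back-up mode and damaged silicone coating. The housing fault is seen before the device is in the patient. None meets 18.1 unless something also happens to the patient, yet 18.7 assesses all of them as ADEs.

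**What follows.**

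1. If sites follow 18.3, a tally of DD forms omits cases 3, 4 and 5, which are all the faults that caused an AE. If they also follow 9.8, it omits deficiencies found at interim visits.
2. If sites follow 18.7, case 2 faults enter the ADE tally although nothing happened to the patient.
3. The deadline is in doubt only for faults with SADE potential in cases 2 and 4. Cases 1, 3 and 5 have the same deadline on every reading.

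**The case against.** Much can be said for the plan. Section 18.3 is a complete allocation: every fault has a form, and an AE caused by a malfunction is already an ADE under 18.2, so no harmful fault goes unrecorded. Section 18.7 is a risk list that names no form and no deadline; it becomes a recording rule only through the sentence in 18.8.1 that sends ADEs to the AE form. A careful reader would let the definitions in 18.1 and 18.3 govern. Other parts of the CIP are neutral: 9.3.1 and 9.4 refer to the respective form, and 9.7 allows either or both. A cautious site could file both forms and satisfy 18.3 and 18.8.1 together.

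This limits the point but does not remove it. Nothing tells sites to file both forms or which section prevails, and 9.8 contradicts 18.3 for a deficiency without an AE.

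Two stronger readings are tempting, and the documents do not support them.

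- *The 24-hour deadline is lost.* Table 5 is keyed to the type of event, and 18.3 applies SADE potential to any deficiency, so a site can properly apply 24 hours. Section 18.9 also carries a general duty to report serious deficiencies without unjustified delay, though with no form or hours named. The deadline is ambiguous, not removed.
- *The reported deficiency rate will omit the harmful faults.* That holds only if deficiencies are counted from DD forms. The SAP leaves the count to a vigilance report whose method is not described, and a deficiency flag on the AE form cannot be ruled out.

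**Conclusion.** The sections conflict and should be reconciled. Sites can file the same fault differently, so DD and ADE counts may not be comparable across sites. A count from DD forms alone would leave out the faults that caused an AE. Whether the 24-hour or the two-week row applies is unclear for a fault with SADE potential that also caused a non-serious AE, or that is listed in Table 4 and caused no AE. Faults that caused a serious AE keep 24 hours.

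The primary endpoint is not directly affected, because SADEs are recorded on the AE form under every reading and are then adjudicated. What is touched is data of interest and the timeliness of some reports.

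No numerical size can be given. A reader might scale up the one failed insertion from a bent tool among 92 patients in the predecessor study (CIP 5.2.4). That was a tool from a different insertion set, and it is not stated to have caused an AE. The documents also give no transmission failure rate from which to estimate extra ADEs. The conclusion rests on the wording of the sections and on the assumption that some sites will follow one section and some another.

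**What to change.** Reconcile CIP 9.8, 18.3, 18.7, 18.8.1 and Table 5 to a single recording rule. One workable version:

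1. Every device deficiency gets a DD form with the SADE-potential assessment, at scheduled and interim visits alike. When an AE resulted, an AE form is added and linked to it.
2. The text before Table 4 states that the technical faults listed there are ADEs only if they meet 18.1, and are otherwise device deficiencies.
3. Table 5 states that its existing timeline for deficiencies with SADE potential applies whether or not an AE occurred. No new deadline is created.
4. SAP section 15 states that the deficiency count includes deficiencies with and without a linked AE, and names the source of the count.

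The cost is an amendment to the CIP wording, a sentence in the SAP, and one extra short form for the few deficiencies that also caused an AE. Both forms already exist.
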